### Sensitivity analysis

No prespecified sensitivity analyses will be performed. Additional post-hoc sensitivity analysis will be considered as appropriate later.

Line plots will be included to depict responder-type of endpoints of SALT for each treatment group. The X-axis will feature visits, and the Y-axis will represent the proportion of participants, expressed as a percentage.

### **5.7.3 Analysis of Other Exploratory Efficacy Variables**

All the continuous exploratory variables will be analyzed using descriptive statistics (n, mean, median, standard deviation, minimum, and maximum).

All the binary exploratory variables will be summarized with frequency and percentages.

Intercurrent events will be handled as described in section [5.7.1](#) and [5.7.2.2](#) based on the characteristics of the analysis variable. No additional missing data imputations and sensitivity analysis are applicable for other exploratory endpoints.

## **5.8 Analysis of Safety Data**

The summary of safety data will be performed based on safety analysis set.

The safety analysis will be based on the reported AEs, clinical laboratory evaluations, physical examination, vital signs, and 12-lead ECG.

### **5.8.1 Analysis of Adverse Events**

Incidence tables for both non-TEAEs and TEAEs will be presented for each treatment group and collectively for the combined IMG-007 group. TEAEs will be classified into two groups as follows:

- TEAEs occurred through the 24 weeks of study period: TEAEs with the starting date between the date of first treatment administration and week 24 visit (or end of study, if achieved prior to week 24 visit) will be considered here.
- TEAEs occurring through the 36 weeks of study period: TEAEs with starting between the date of first treatment administration and week 36 visit (or end of study, if achieved prior to week 36 visit) will be considered here.

The table will include the number (n) and percentage (%) of participants who are experiencing an adverse event, along with the corresponding number of episodes of AEs. Participants with multiple adverse events in a particular category will be counted only once in that category.

Participants with multiple severities/grading will be counted only once under maximum severity/grading.

The number and proportion of participants reporting non-TEAEs/TEAEs will be summarized, sorted by decreasing frequency of SOC and PT in the combined IMG-007 group, and in case of ties, then sorted by decreasing frequency of SOC and PT in the IMG-007 [REDACTED] group, and finally, in case of further ties, then alphabetically.

Listings will be provided by SOC and PT, for non-TEAEs, TEAEs and TESAEs, TEAEs of infusion related reactions, and TEAEs leading to study treatment discontinuation.

The following summaries will be provided for the adverse events by treatment group.

- Overall summary of AEs during the 24-Week Period: The overall summary of AEs will be provided with number and proportions of participants with any:
  - non-TEAE
  - TEAE
  - Related TEAE
  - SAE
  - TEAE by CTCAE grades
  - TEAE that are infusion related reaction
  - TEAE leading to 4-week dosing period discontinuation
  - TEAE leading to 16-week dosing period discontinuation
  - TEAE leading to study discontinuation
  - TEAE with outcome of death
- Overall summary of AEs during the 36 weeks of study period: The overall summary of AEs will be provided with number and proportions of participants with any:
  - TEAE
  - Related TEAE
  - SAE
  - TEAE by CTCAE grades
  - TEAE leading to study discontinuation
  - TEAE with outcome of death
- Summary of non-TEAEs by SOC and PT
- Summary of TEAEs by SOC and PT during 24-Week period
- Summary of TEAEs by SOC and PT during 36-Week period
- Summary of TEAEs occurring for at least 2 participants in any of the treatment group by PT during 24-Week period
- Summary of TEAEs occurring for at least 2 participants in any of the treatment group by PT during 36-Week period
- Summary of Serious TEAEs by SOC and PT during 24-Week period
- Summary of Serious TEAEs by SOC and PT during 36-Week period
- Summary of TEAEs by PT and worst CTCAE grade during 24-Week period
- Summary of TEAEs by PT and worst CTCAE grade during 36-Week period
- Summary of TEAEs with CTCAE grade 3 or higher by PT during 24-Week period
- Summary of treatment related TEAEs by SOC and PT during 24-Week period
- Summary of treatment related TEAEs by SOC and PT during 36-Week period

- Summary of TEAEs leading treatment discontinuation by SOC and PT during 24-Week period
- Summary of TEAEs leading to death by SOC and PT during 24-Week period

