3 STUDY OBJECTIVES AND ENDPOINTS

Study objectives and endpoints are summarized in [Table 3](#).

Table 3 Study Objectives and Endpoints

Primary Objective	Primary Endpoint
To evaluate AEs emergent from multiple doses of IMG-007 in adult participants with AA	Incidence of TEAEs
Secondary Objectives	Secondary Endpoints
To evaluate the efficacy of multiple doses of IMG-007 in AA participants as measured by SALT at Week 24	Percentage change in SALT from baseline to Week 24
Exploratory Objectives	Exploratory Endpoints
To further evaluate the efficacy of multiple doses of IMG-007 in AA participants as measured by SALT and other investigator's assessments and patient reported outcomes	
• Absolute and percentage changes from baseline in SALT by visit• Proportion (%) of participants achieving a 30% improvement in SALT score (SALT30) by visit 

Abbreviations: AA = alopecia areata; AAPPO = Alopecia areata patient priority outcomes; ADA = anti-drug antibody; AE = adverse event; CL = central compartment clearance; EB = eyebrows; ECG = electrocardiogram; EL = eyelashes; FN = fingernails; HADS = Hospital anxiety and depression scale; IATS = Investigator's assessment of a target scalp lesion; IGA = Investigator's global assessment; PD = pharmacodynamic; PGIC = patient global impression of change; PGIS = patient global impression of severity; PK = pharmacokinetic; S = scalp; SALT = Severity of Alopecia Tool; TEAE = treatment-emergent adverse event; Vc = central compartment volume

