8.1.3 Adverse Event Variables

The following variables will be collected for each AE:

- AE (verbatim)
- The date when the AE started and stopped
- The maximum severity reported or changes in severity (report only the maximum severity for a calendar day). See [Section 8.1.4](#) for severity assessment.
- Whether the AE is serious or not
- Investigator causality rating against the study treatment (yes or no). See [Section 8.1.5](#) for causality assessment.
- Action taken with regard to study treatment
- Administration of treatment for the AE
- Outcome

In addition, the following variables will be collected for SAEs, either on the eCRF or SAE reporting form:

- Date the AE meeting the criteria for SAE (SAE onset date)
- Date the investigator becoming aware of the SAE
- Seriousness criteria
- Date of hospitalization
- Date of discharge
- Probable cause of death

- Date of death
- Whether an autopsy was performed
- Causality assessment in relation to study procedure(s)
- Causality assessment in relation to other medication
- Description of the SAE

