11.3 Statistical Analysis

11.3.1 Analysis of Safety

Safety variables including incidence, severity, and changes from baseline of relevant parameters (such as vital signs, ECGs, and clinical laboratory values) will be summarized.

- AEs will be coded using the Medical Dictionary for Regulatory Activities (MedDRA, the version currently in use by the Sponsor at the time of database lock). TEAEs are defined as events started after the initiation of the first dose of study treatment or events present that worsen after the start of dosing. The number and proportion of participants experiencing one or more TEAEs will be summarized by severity, and relationship to study treatment.
- Prior and concomitant medications will be coded using the World Health Organization Drug Dictionary. The number and proportion of participants taking prior and/or concomitant medications will be summarized.
- Vital signs (systolic and diastolic blood pressure, pulse, respiratory rate, and temperature) and ECG parameters will be summarized by visit descriptively. Changes from baseline, number, and proportion of participants with clinically important values will be presented descriptively.
- Clinical laboratory parameters, including changes from baseline, where appropriate, will be summarized using descriptive statistics, by post-dosing shift from baseline in the normal or abnormal category of laboratory values by visit, and number and proportion of participants with a treatment-emergent clinically significant abnormal value based on predefined criteria, and data listings.

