## 4.6 Safety Variables

### 4.6.1 Adverse Events and Serious Adverse Events Variables

Adverse events and serious adverse events will be collected from the time of informed consent signature until the end of the study. All adverse events will be coded according to the latest available version (26.0 or higher) of MedDRA.

An **Adverse Event** is the development of any untoward medical occurrence in a participant or clinical study participant who is administered with a medicinal product that does not necessarily have a causal relationship with this treatment. An AE can therefore be any unfavorable and unintended sign, symptom, or disease temporally associated with the use of a medicinal product, whether or not considered related to the medicinal product, including the following conditions:

- 1) Any newly occurred undesirable medical condition (including newly diagnosed disease or signs and symptoms when a diagnosis is pending);
- 2) Exacerbation of a chronic or intermittent pre-existing condition including either an increase in frequency and/or intensity of the condition. However, events that are unequivocally due to natural disease progression of the underlying disease being studied should not be reported as an AE during the study unless judged by the investigator to be more severe than expected for the participant condition;
- 3) Clinically significant laboratory abnormality.

A **Serious Adverse Event** is defined as any untoward medical occurrence that, at any dose, meets one or more of the criteria listed:

- **Results in death**
- **Is immediately life threatening**
- **Requires in-patient hospitalization or prolongation of existing hospitalization**
- **Results in persistent or significant disability or incapacity**
- **Is a congenital abnormality or birth defect**
- **Is an important medical event** (i.e., that may jeopardize the participant or may require medical treatment to prevent one of the outcomes listed above.)

Details for each criterion above are presented in the study protocol section 8.1.2.

**Non-treatment emergent AEs** are AEs that are developed or worsened in severity compared to the baseline during the period between participant enrolment and the first study drug administration. All AEs collected during the screening period are considered as non-TEAEs.

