**Treatment-emergent AEs (TEAEs)** are AEs that developed or worsened in severity compared to the baseline during the treatment and follow-up period (including the extended follow-up). As only the worsening pre-existing AEs and new AEs reported during the treatment and follow-up period (including the extended follow-up) will be collected in the study, all AEs collected

during the treatment and follow-up period (including the extended follow-up) are considered as TEAEs.

**TEAE that are infusion related reaction** will be summarized. Localized injection/infusion reactions that may include pruritus, pain, erythema, swelling, rashes, or bleeding around the injection/infusion site. Systemic injection/infusion-related reactions may be immediate type or delayed type immune complex-associated hypersensitivity reactions (e.g., serum sickness).

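### By definition, a screening AE that worsens after the first infusion is a TEAE, but the SAP's sorting rules would leave it out of the 24- and 36-week summaries if it stays on its original record

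*SAP*

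**What the plan says.** The primary endpoint in Protocol section 3 is "Incidence of TEAEs".

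Both documents include worsening in the definition of a TEAE. Protocol 11.3.1 covers "events started after the initiation of the first dose of study treatment or events present that worsen after the start of dosing". SAP 4.6.1 says that TEAEs "are AEs that developed or worsened in severity compared to the baseline during the treatment and follow-up period", and it includes the extended follow-up in that period.

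Two SAP rules then decide where an event is counted:

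- SAP 4.6.1, on screening: "All AEs collected during the screening period are considered as non-TEAEs". No exception is made for an event that later worsens.
- SAP 5.8.1, on the summaries: the 24-week group takes "TEAEs with the starting date between the date of first treatment administration and week 24 visit". The 36-week group uses the same kind of rule up to the Week 36 visit. Neither mentions a date of worsening.

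On recording, Protocol 8.2.1 collects AEs from consent, and screening can last up to 35 days. Protocol 8.1.3 lists the start and stop dates of each AE among the variables, together with "The maximum severity reported or changes in severity (report only the maximum severity for a calendar day". It names no date-of-worsening field.

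**The concern.** The definition and the sorting rules use different tests. The definition asks whether an event began or got worse after dosing. The sorting rules ask when it was collected and when it started. The two agree for a new event. They can disagree for an event already open at first dose that later rises in grade, because such an event can have a pre-dose start date and still meet the definition.

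What is at stake is the count behind the primary endpoint. The participant would be missing from the overall TEAE row only if there were no other TEAE. The event itself would be missing from the summaries by preferred term, grade and relatedness in any case. A Grade 1 screening event that reached Grade 3 after an infusion would be missing from the Grade 3 or higher table, which SAP 5.8.1 lists for the 24-week period. Two programmers following the SAP in good faith could report different primary-endpoint counts.

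**Working it through.** The documents give no figure to reproduce, because this is a question of event classification. The check applies the stated rules to one event under each way it could be recorded, and then sizes the result.

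**Inputs.** First dose is Day 1, the Week 24 visit is Day 169 and the Week 36 visit is Day 253 (schedules of assessments, nominal days). Cohort sizes are 6 and 24, 30 in total (Protocol 4.1). The event is an illustration: onset on Day -10 in screening, with a rise in grade on Day 20.

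**Step 1: the definition.** The event was present before dosing and worsened after it. It is a TEAE under Protocol 11.3.1 and under the SAP 4.6.1 definition.

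**Step 2: the SAP 5.8.1 windows**, that is, Day 1 ≤ starting date ≤ Day 169 (24 weeks) or Day 253 (36 weeks).

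- One record that keeps its onset date: the starting date is Day -10, which is before Day 1. The event is outside both windows and is not counted.
- A new record opened at worsening: the starting date is Day 20, and 1 ≤ 20 ≤ 169 ≤ 253. The event is inside both windows and is counted.

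**Step 3: the SAP 4.6.1 collection rules.**

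- One record: it was collected in screening, so the screening sentence makes it a non-TEAE.
- New record: it is collected in the treatment period, so the SAP counts it as a TEAE.

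The two sets of rules therefore agree with each other in each case. In the one-record case both contradict the definition, so changing the window in 5.8.1 alone would not be enough.

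**Step 4: which recording applies?** Protocol 8.1.3 lists changes in severity as a variable of an AE, which fits one record. It does not say that the change stays on that record, nor that the original start date is kept. Neither document contains a rule on opening a new record, so the question stays open.

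**Step 5: size.** Let k be the number of participants whose only TEAE is a worsened screening AE on one record. The understatement of incidence is 100 × k/n points. For k = 1:

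- Cohort 1: 100 × 1/6 = 16.7 points
- Cohort 2: 100 × 1/24 = 4.2 points
- Pooled: 100 × 1/30 = 3.3 points

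If the participant has any other counted TEAE, the change in overall incidence is 0, and only the preferred-term, grade or relatedness rows can change. The documents give no basis for estimating k.

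**The case against.** The strongest reply is that the SAP already presumes the harmless recording method. Directly after its TEAE definition it reasons "As only the worsening pre-existing AEs and new AEs reported during the treatment and follow-up period" will be collected, and concludes that everything collected in that period is a TEAE. Protocol 8.1.1 likewise treats an exacerbation of a pre-existing condition as an AE in its own right. On that reading a worsened event gets its own record and start date, and both windows catch it. The CRF instructions, which are not in these documents, may say exactly this.

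This stands in part. It makes the loss conditional. It does not close the gap, because the SAP sentence is a premise about what will be collected rather than an instruction to sites. The protocol's text on exacerbation does not say what to do with an AE record that has been open since consent.

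Three stronger readings are tempting, and the documents do not support them.

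- *Such events are certainly dropped.* That needs the one-record method, which neither document prescribes.
- *Every AE table is affected.* The non-TEAE table and the listings are not selected by these windows, the SAE row is not labelled as a TEAE row, and the interim and SRC output lists (SAP 7.1.1 and 11.5) do not restate the windows.
- *The plan always makes the drug look safer.* Under one-record entry this mechanism can only remove TEAEs; under new-record entry it has no effect. Other SAP conventions lean the conservative way. A partial or missing start date that could be post-dose, with a stop date on or after first dose, is set to the first-dose date (SAP 11.2). Missing intensity is treated as severe and missing relationship as related (SAP 6.2). The start-date convention does not help a fully dated event, for which no action is taken.

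It is also fair to say that the 1/n figures are the upper end for each affected participant. In the single-dose healthy-participant study (Protocol 2.2), 34 of 44 had at least one TEAE, so 10/44 = 22.7% had none. Suppose, as an assumption only, that the same share of affected participants here would have no other TEAE. The expected shift per affected participant is then 16.7 × 0.227 = 3.8 points in Cohort 1, about 0.9 in Cohort 2 (100/24 × 10/44) and 0.8 pooled (100/30 × 10/44). That study enrolled a different population and its data were blinded active plus placebo, so this is an illustration and not an estimate.

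**Conclusion.** The point holds as a conditional inconsistency in how the primary endpoint is counted. The agreed definition includes "events present that worsen after the start of dosing", while the screening sentence in SAP 4.6.1 and the starting-date windows in SAP 5.8.1 would exclude such an event if it began in screening and stayed on its original record. If worsening opens a new record, nothing is lost.

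The size is at most 16.7, 4.2 or 3.3 points (Cohort 1, Cohort 2, pooled) for each participant whose only TEAE is such an event, and zero for overall incidence otherwise. These figures assume the planned cohort sizes, a complete pre-dose start date and one-record entry. The frequency is unknown. No hypothesis test on TEAEs is planned, so no test result depends on this. It warrants a clarification because the risk to the primary endpoint runs in one direction and is cheap to remove.

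**What to change.** Make two edits to the SAP, before database lock.

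1. In 5.8.1, apply the 24- and 36-week windows to a TEAE date: the later of onset and the first post-dose rise above the grade held at first dose. For an event that begins after the first dose there is no grade held at first dose, so its TEAE date is its onset. For an event already open at first dose, it is the date of that rise; with no rise, the event remains a non-TEAE. Alternatively, state that worsening of an open AE is recorded as a new AE starting on the day it worsened, and confirm that the CRF instructions say the same.
2. In 4.6.1, add to the screening-AE sentence: *unless they worsen after the first dose*.

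The first option needs dated severity changes in the database. If only the maximum severity is held, the date cannot be derived and the new-record rule is the workable one.

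The cost is one derived date and two sentences. TEAE counts may rise slightly. The agreed TEAE definition does not change, and the count it requires is obtained under either recording method.

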The study includes a 16-week treatment period and an 20-week follow-up period. The proposed 16-week treatment period is based on a 4-week dosing duration, which is estimated to result in a reasonable level of IMG-007 systemic exposure by Week 16 (i.e., 12 weeks after the last dose of study treatment at Week 4) when a clinically meaningful improvement in scalp hair loss is anticipated (see Section 2.5.2). Based on the observation that treatment with mAbs against OX40 for as short as 4 weeks provided clinically meaningful and durable improvements in AD symptoms for up to 18 weeks after the last dose of study treatment ([Guttman-Yassky et al 2019](#); [Nakagawa et al 2020](#); [Guttman-Yassky 2023](#)). Recent phase 2b study of amlitelimab, an anti-OX40L antibody, showed a durable clinical response for up to 28 weeks after drug withdrawal, despite minimal remaining serum concentrations of study drug ([Weidinger et al 2024](#)). A similarly enduring clinical effect may be expected for OX40/OX40L antagonism in AA, even with low drug exposure. Moreover, clinical studies in AA have shown that onset to visible hair regrowth was generally slow especially for targeted biologics; hence most trials evaluate key efficacy endpoints at Week 24 and Week 36 ([King et al 2021](#), [Guttman-Yassky et al 2022](#)). Based on the above considerations, the timing of the secondary efficacy assessment has been revised from Week 16 to week 24, and an extended follow-up period post EOS was added to assess potential further clinical improvement beyond Week 24 up to Week 36. Separately, the follow-up period can help assess the duration and reversibility of potential TEAEs, especially those with a late onset.

The efficacy measurements included in this study are typically used for assessing disease activity in adult AA participants. The key variables include SALT score, other investigator's assessments, and patient reported outcomes. The clinical and laboratory assessments for safety and tolerability in this study are standard and generally accepted in clinical trials with a similar target population.

[figure not shown]

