The extended follow-up period after EOS consists of two visits: Week 30 (Day 211) and Week 36 (Day 253).

The schedule of assessments (SoA) at each visit is summarized in [Table 1](#). Assessments of efficacy, safety will be conducted throughout this study (until extended follow-up period post EOS) and PK, PD, and immunogenicity data will be collected until the end of EOS visit.

Participants who discontinue treatment early (before completing the 4-week dosing period) should continue with all the remaining study visits.

Participants who withdraw from the study any time before the Week 16 visit should complete the Week 16 (Day 113)/EOT visit at withdrawal.

Participants who withdraw from study early during the follow-up period should complete the Week 24 (Day 169)/EOS visit at withdrawal.

Participants who discontinue early after the Week 24/EOS visit but before the Week 36 visit should complete Week 36 (Day 253) visit at withdrawal.

A participant who withdraws from the study prior to receiving two doses of study treatment (i.e., completing the Week 2 visit) for reasons other than AEs will be replaced.

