6.10 Early Withdrawal from Study

6.10.1 Discontinuation of Study Treatment

6.10.1.1 Permanent Discontinuation of Study Treatment

[REDACTED]

[REDACTED]

[REDACTED]

[REDACTED]

[REDACTED]

[REDACTED]

[REDACTED]

- [REDACTED]
- [REDACTED]
- [REDACTED]
- [REDACTED]
- [REDACTED]
- [REDACTED]
- [REDACTED]

- Participant receives an investigational drug (other than IMG-007)
- Lack of efficacy/activity of the study treatment, defined as inadequate improvement in disease activity based on investigator's clinical judgment
- Physician decision
- Study is stopped by the Sponsor or health authority.

Note that discontinuation of study treatment does not represent withdrawal from the study. If study treatment is discontinued early, efforts should be made to perform the remaining study visits through EOS.

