11.3.7 Interim Analysis

A first interim analysis (IA) may be performed when all participants have completed the Week 24 (Day 169) visit or discontinued early prior to Week 24 visit. A second IA may be performed when all participants have completed the Week 30 (Day 211) visit or discontinued early prior to Week 30 visit.

Final analysis will be performed when all participants have completed the study (i.e., Week 24 [Day 169]/EOS visit or the Week 36 [Day 253] visit, as applicable) or discontinued early. Details of the IA and the final analysis will be provided in the SAP.

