## 5. STATISTICAL METHODS

For continuous variables, at the reported visits or in overall summary, descriptive statistics will consist of: number of non-missing observations (n), mean, median, standard deviation (SD), minimum, and maximum. It is to be noted that number of participants with observations could include participants with data that were observed as well as those that were imputed for specific types of missing data or determined based on handling of intercurrent events, as explained in later sections.

For categorical variables, frequencies and percentages will be displayed for each category.

In the context of efficacy-related tables, percentages will be calculated based on the denominator of number of participants with data depending on the handling of intercurrent events as well as imputations of missing data as explained in the later sections. For non-efficacy tables, percentages will be calculated based on the corresponding analysis population unless otherwise specified in the mock shell.

Listed below are some subgroups for potential exploratory subgroup analysis:

- Race (Black/African American vs. Non-Black/Non-African American)
- Age group (<30 years old vs.  $\geq 30$  years old)
- SALT Score at baseline (50 to <75, 75 to <95, 95 to 100)
- Age at disease onset ( $\leq 12$  years old vs.  $> 12$  years old)
- Presence of autoimmune comorbidities (Yes vs. No)
- Presence of atopic comorbidities (Yes vs. No)
- Duration of current episode (< 2 years vs.  $\geq 2$  years)
- Baseline elevated IgE (Yes vs. No)

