## 5.5 Participant Disposition

Summaries will be provided for the following data in each treatment group for the full study sample (i.e., all screened participants who signed informed consent):

- The number and percentage of participants screened, and who failed screening, along with the reasons for screen failure. (This will be reported only in the overall group.)
- The number and percentage of participants included in each treatment group as well as in each study analysis set.
- The number and percentage of participants who completed the 4-week dosing period, discontinued the 4-week dosing period with the reason for discontinuation, completed the 16-week treatment period, discontinued 16-week treatment period with reason for discontinuation, completed the study, and discontinued the study with reason for discontinuation, consented for the extended follow-up, completed the extended follow-up, and discontinued the extended follow-up with reason for discontinuation.

A summary will be provided for major protocol deviations by deviation category and treatment group for the safety analysis set. The protocol deviations flagged as ‘CSR Reportable’ will be classified as major protocol deviations.

The following listings will be provided.

- The participant disposition listing comprises various details, including the date of informed consent form (ICF) signing, ICF and protocol versions, enrolment or screen failure dates, and the completion/discontinuation date of the 4-week dosing period, date of 16-week treatment period/discontinuation, reason for discontinuation, study completion status, date of study completion, among other factors.
- A listing of screen failures with inclusion criteria not met and/or exclusion criteria met.
- Listing of protocol deviation.

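### If some participants do not enter or complete the extended follow-up, the 36-week TEAE percentages will understate events first appearing after Week 24; SAP 5.8.1 plans no table based on those actually observed.

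*SAP*

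**What the plan says.** The primary endpoint is the incidence of TEAEs, with no time window (Protocol Section 3, Table 3). SAP 5.8.1 reports TEAEs over two windows, 24 and 36 weeks. The longer one takes events starting "between the date of first treatment administration and week 36 visit (or end of study, if achieved prior to week 36 visit". Six summaries use it: overall, by SOC and PT, in at least two participants, serious, by worst grade, and related. Each gives participants (n and %) and episodes.

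On the denominator, SAP 5.8 states: "The summary of safety data will be performed based on safety analysis set". That set is all participants with at least one dose (SAP 3.1). SAP 5 adds: "For non-efficacy tables, percentages will be calculated based on the corresponding analysis population unless otherwise specified in the mock shell".

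On who is observed after Week 24, SAP 5.5 tabulates, apart from study completion, those who "consented for the extended follow-up, completed the extended follow-up, and discontinued the extended follow-up with reason for discontinuation". Protocol 11.3.7 defines completion for the final analysis as "Week 24 [Day 169]/EOS visit or the Week 36 [Day 253] visit, as applicable". Protocol 2.5.1 says the extension was added in a revision, mainly to look for further clinical improvement, and also that "the follow-up period can help assess the duration and reversibility of potential TEAEs, especially those with a late onset".

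**The concern.** The 36-week tables treat every dosed participant as observed to Week 36. Anyone whose participation ends at Week 24 stays in the denominator, cannot contribute a later event, and so counts as event-free. The affected window, Day 169 to Day 253, is 84 of the 252 days after baseline, one third of the total. It is also where late-onset events would be seen.

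The SAP plans no table restricted to onset after Week 24, no denominator of participants observed in that window, and no rate per participant-time. It also does not say which window is the main result for the primary endpoint.

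**Working it through.** The documents give no TEAE rate for this population, no extension-entry fraction and no precision statement for TEAEs (the sample-size text is blacked out). There is no planned figure to reproduce, and what follows is illustration.

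**Inputs.** From the documents: Cohort 1 has 6 participants and Cohort 2 has 24, 30 in total (Protocol 4.1). Assumed: *c*, the fraction observed through the extension, taken as unrelated to risk; *q*, the risk of a first onset in Weeks 24 to 36 among those without the event by Week 24; and *p*, the incidence by Week 24.

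**Formulas.** With complete follow-up, incidence = p + (1 − p)q. Under the default rule, reported incidence = p + (1 − p)q·c. The late component is therefore reported at c times its value.

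**Results, q = 20%:**

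| Type of TEAE | c = 100% | c = 75% | c = 50% | c = 25% |
|---|---|---|---|---|
| First appears after Week 24 (p = 0) | 20% | 15% | 10% | 5% |
| Already 10% by Week 24 | 28.0% | 23.5% | 19.0% | 14.5% |

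**Any-TEAE rate.** For an illustrative p, take 77.3% from the healthy-participant study (34 of 44, Protocol 2.2).
- q = 20%: complete 0.773 + 0.227 × 0.20 = 81.8%; at c = 50%, 0.773 + 0.227 × 0.20 × 0.5 = 79.6%. The shift is about 2 points.
- q = 10%: 79.6% against 78.4%, about 1 point.
- Upper sensitivity case, with the hazard constant over all 36 weeks: 1 − 0.227^1.5 = 89.2% against 83.2% at c = 50%, 6 points.

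**Precision when no late event is seen.** The exact one-sided 95% upper limit is 1 − 0.05^(1/n).
- All participants: 9.5% if 30 are observed, 18.1% if only 15 are.
- Cohort 1: 39.3% if 6 are observed, 63.2% if 3 are.

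The default table would show N = 30, or N = 6 for Cohort 1, in either case.

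**Unequal entry, hypothetical.** If 3 of 6 enter in Cohort 1 and 24 of 24 in Cohort 2, the same 20% late risk appears as 0.20 × 3/6 = 10% against 20%. With those who entered as denominator it is 20% in both.

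**The cut-off term.** Protocol 7.1.5 places the EOS visit at Week 24. Protocol 4.2 ends the study after the extended follow-up visits, discontinuation or loss to follow-up. SAP 5.8.1 uses end of study in both windows without saying which is meant. SAP 4.6.1 collects AEs to the end of the study, where Protocol 8.2.1 says through the extended follow-up.

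**Treatment discontinuers.** Protocol 4.1.2 says: "Participants who discontinue treatment early (before completing the 4-week dosing period) should continue with all the remaining study visits". Protocol 6.10.1.1 says: "efforts should be made to perform the remaining study visits through EOS". With EOS at Week 24, the second stops short of the first.

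**The case against.** The current protocol presents the extension as one of four periods for each cohort (4.1.2), says participants will return for it (7.1.6), and never calls it optional. The consent count in SAP 5.5 may only record the re-consent that Protocol 12.3 requires after an amendment. Crude incidence on the safety set is conventional, the mock shell may change the denominator, and the disposition table will show by treatment group how many consented to and completed the extension.

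Much of this stands. It makes the bias conditional and lets a careful reader spot it. It does not explain why completion may be at Week 24 where applicable. Nor can disposition counts recover the late incidence in full: each participant counts once per category, so subtracting the 24-week table from the 36-week table misses anyone with an event in the same category in both periods.

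Three stronger readings are tempting.
- *Late TEAEs are understated.* This needs incomplete entry or completion, and the documents give no fraction.
- *A difference between doses would be an artefact.* Cohorts start in sequence and the extension came later, so unequal entry is possible. But no enrolment dates are given and the amendment logs are blacked out. The one clue is weak and points the other way: the SRC analysis document is dated 11 April 2024 (SAP 8). If the last Cohort 1 Week 2 visit was near then (an assumption), that participant's Week 24, 22 weeks later, falls in mid-September, after the protocol date of 2 August 2024. No between-dose safety test is planned, and six participants could not support one for late events.
- *The 36-week window collapses to Week 24 because EOS is Week 24.* Protocol 4.2 and the TEAE definition in SAP 4.6.1 both include the extension. The 24-week window also provides for end of study before the Week 24 visit, which would make no sense on that reading. The term is ambiguous and needs clarifying; it is not uniformly Week 24.

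On treatment discontinuers, the all-visits instruction recurs in the synopsis, Table 1 footnote 21 and Section 6.6, while Section 6.10.1.1 is partly blacked out. Loss of these participants after Week 24 is not established, but the two statements still differ.

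**Conclusion.** The point holds conditionally. By default the 36-week percentages use all dosed participants, and the documents foresee that some may not be observed after Week 24. If so, the incidence of TEAEs first appearing after Week 24 is understated by the fraction not observed: half entry reports half the rate. With full entry and completion the bias is zero.

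Extension entry does not affect the 24-week tables. The any-TEAE rate would probably move by 1 to 2 points at half entry, and by about 6 if the event rate did not fall over time; both rest on a borrowed 77.3% and assumed late risks. The material effect is on individual late-onset terms and on how much reassurance a zero count gives. A difference in entry between doses is possible but not shown. This is a cheap improvement and does not invalidate the primary analysis.

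**What to change.** In SAP 5.8.1:
1. Name the 24-week table as the main result for the primary endpoint.
2. Add a table of TEAEs with onset after the Week 24 visit, by cohort, with participants who entered the extended follow-up as denominator, or events per participant-weeks observed, or both. State the number who entered in the header.
3. In both window definitions, replace end of study with 'last study contact', and align the collection period in SAP 4.6.1 with Protocol 8.2.1.

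Separately, Protocol 6.10.1.1 and 4.1.2 must be reconciled on how far treatment discontinuers are followed.

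The cost is SAP wording and one table. The late-event percentage will rest on a smaller denominator and may look less favourable. The added table does not correct for selection if those who enter differ in risk from those who do not. With full entry and completion, the existing percentages do not change.
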